5.4.1. Safety Tables Presentation

There are 3 DBLs in this study, respectively, at Week 24, Week 52, and End of Study (Week 112). Depending on the safety data categories, the cumulative safety data will be analyzed through different study periods which include, but are not limited to, through Week 24 and through end of study periods. Tabular summaries of safety events for key study periods are in general presented as follows:

5.4.1.1. Summaries Through Week 24

Safety data through Week 24 will be analyzed according to the following intervention groups:

- 1. **Placebo**: Participants who received placebo only and no guselkumab prior to Week 24.
- 2. **Guselkumab 100 mg at Weeks 0, 4, and then q8w**: Participants who received guselkumab 100 mg q8w prior to Week 24 with an additional dose at Week 4.
- 3. **Guselkumab 100 mg q4w**: Participants who received guselkumab 100 mg q4w prior to Week 24.
- 4. **Guselkumab Combined:** Participants in Groups 2 and 3.

The above intervention groups 1-3 are **mutually exclusive**. This allows between-group comparisons of safety between a guselkumab group and the placebo group based on similar follow-up period in each group. The safety tables will have the column headings below:

		Guselkumab		
	Placebo	100 mg q8w	100 mg q4w	Combined
Analysis set: Safety Analysis Set	###	###	###	###

For participants who started treatment with placebo only but later received any amount of guselkumab prior to Week 24 inadvertently, the safety events/measurements on and after the first dose of guselkumab, will be excluded from the data summaries through Week 24. Only the safety events/measurements that occurred while the participants had been receiving placebo only will be included in the data summaries through Week 24.

5.4.1.2. Summaries Through Week 52

Safety data through Week 52 will be analyzed according to the following intervention groups:

- 1. **Placebo:** Participants who received placebo only. Follow-up will be based on the period that the participant was on placebo from the first dose up to Week 52.
 - a. For participants who started treatment with placebo and later received treatment with guselkumab (due to CO or inadvertently), follow-up will end at the first dose of guselkumab, and only the safety events/measurements that occurred prior to the first dose of guselkumab will be included in this group.

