- 2. Placebo → Guselkumab 100 mg q4w: Participants who started treatment with placebo and later received treatment with guselkumab (due to CO or inadvertently). Follow-up will start from the first dose of guselkumab up to end of study. All the safety events/measurements that occurred on and after the first dose of guselkumab up to end of study will be included in this group.
- 3. **Guselkumab 100 mg at Weeks 0, 4, and then q8w**: Participants who received guselkumab 100 mg q8w prior to Week 24 with an additional dose at Week 4. Follow-up will be from the first dose up to Week 52.
- 4. **Guselkumab 100 mg q4w**: Participants who received guselkumab 100 mg q4w prior to Week 24. Follow-up will be from the first dose up to end of study.
- 5. **Guselkumab 100 mg q4w Combined:** Participants in Groups 2 and 4.
- 6. All Guselkumab Combined: Participants in Groups 2, 3, and 4.

The above intervention groups 1-2 are **not mutually exclusive**. The safety tables will have the column headings below:

	Guselkumab					
		Placebo				
	\rightarrow 100			100 mg q4w	All	
	Placebo	100 mg q4w	100 mg q8w	100 mg q4w	Combined	Combined
Analysis set: Safety Analysis Set	###	###	###	###	###	###

CONFIDENTIAL – FOIA Exemptions Apply in U.S.

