5.4.1.3. Summaries Through End of Study

Safety data through End of Study (Week 112) will be analyzed similarly to safety data through Week 52, replacing Week 52 with End of Study.

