5.4.2. Extent of Exposure and Study Follow-up

The number and percentage of participants who receive study intervention will be summarized. Descriptive statistics for duration study intervention (N, mean, SD, median, and range (minimum, maximum)) will be summarized.

Study intervention duration is defined as (date of last dose of study intervention – date of first dose of study intervention) +1. For the placebo intervention group which has planned crossover at Week 24, the study intervention duration prior to first guselkumab dose will be summarized separately to the study intervention duration on/after first guselkumab dose.

Study follow-up duration is defined in Section 5.4.1.

Study intervention compliance will be summarized descriptively. See Section 6.6 for further details.

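### The SAP's Week 52 safety tables stop q8w follow-up at Week 52 but run q4w to end of study, which would raise crude q4w percentages if programmed as written

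*SAP*

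**What the plan says.** SAP 5.4.1.2 is the section for summaries through Week 52. Its opening sentence sets that scope for every group: "Safety data through Week 52 will be analyzed according to the following intervention groups". The group definitions then give these cut-offs:

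- Group 1 (placebo): Week 52, or the first guselkumab dose if earlier.
- Group 2 (placebo to q4w): end of study, stated twice. "Follow-up will start from the first dose of guselkumab up to end of study" and "All the safety events/measurements that occurred on and after the first dose of guselkumab up to end of study will be included in this group".
- Group 3 (q8w): "Follow-up will be from the first dose up to Week 52".
- Group 4 (q4w): "Follow-up will be from the first dose up to end of study".
- Groups 5 and 6 pool groups 2 and 4, and groups 2, 3 and 4, and take over whatever cut-offs those carry.

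SAP 5.4.1.3 builds the end-of-study tables from this section by "replacing Week 52 with End of Study". SAP 5.4.2 does not define follow-up separately: "Study follow-up duration is defined in Section 5.4.1".

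Under SAP 5.4.3, AE tables give the number and percentage of participants with at least one occurrence, and show average weeks of follow-up per group. SAP 5.4 plans no formal safety comparison. SAP 1.2 triggers the Week 52 lock once every randomized participant has completed Week 52 or left the study.

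**The concern.** The two randomized doses are placed side by side in one table with different stated observation periods. At equal risk, the arm observed longer shows the higher percentage with at least one event. Here that arm is always q4w.

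For the Week 24 tables the SAP gives similar follow-up as the reason groups can be compared: "This allows between-group comparisons of safety between a guselkumab group and the placebo group based on similar follow-up period in each group". That sentence concerns guselkumab against placebo, but the same logic applies to two doses, and the Week 52 definitions as written break it.

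Readers will look at dose. Protocol 2.2.1.1.3 summarizes one-year safety in the earlier studies partly by comparing proportions between q8w and q4w, and reports transaminase increases as slightly more frequent with q4w. An excess caused by longer q4w follow-up would point the same way and could be taken for a dose effect.

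**Working it through.** **Text check.** Four places imply a Week 52 cut: the heading of 5.4.1.2, its scope sentence, and the definitions of groups 1 and 3. The rule in 5.4.1.3 implies it too, because replacing Week 52 by End of Study is only a meaningful step if the source section is cut at Week 52. Three phrases say otherwise: two in group 2 and one in group 4. Section 5.4.2 refers back to 5.4.1, so nothing outside the section settles the conflict.

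**Can later data exist at the Week 52 lock?** Yes. The lock waits for the last participant, so someone enrolled *U* weeks before the last participant can have up to 52 + *U* weeks of data. Whether those data enter the tables depends on the data cut, which the lock trigger does not specify.

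**Size.** The plan has no figure of its own to reproduce. The following is an illustration. From the documents: planned 150 per arm, crossover at Week 24, final visit at Week 112. Assumed: equal constant hazards in both doses, uniform accrual over *A* = 13, 26 or 52 weeks, and Week 52 risk *p* of 10% or 5%.

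With no dropout, risk by week *w* is 1 − (1 − *p*)^(*w*/52). As written, q4w follow-up at the lock is *w* = 52 + *U*, with *U* uniform on 0 to *A* (the 112-week cap is not reached, since 52 + 52 = 104). Averaging over *U*:

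q4w percentage = 1 − (1 − *p*) × (1 − e^(−λA))/(λA), with λ = −ln(1 − *p*)/52.

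For *p* = 10%, λ = 0.10536/52 = 0.002026 per week:

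| A (weeks) | mean q4w follow-up | averaging factor | q4w % | of 150 (q8w: 15) |
|---|---|---|---|---|
| 13 | 52 + 6.5 = 58.5 | 0.9869 | 1 − 0.9 × 0.9869 = 11.2% | 16.8 |
| 26 | 52 + 13 = 65 | 0.9741 | 1 − 0.9 × 0.9741 = 12.3% | 18.5 |
| 52 | 52 + 26 = 78 | 0.9491 | 1 − 0.9 × 0.9491 = 14.6% | 21.9 |

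That is about 1.8, 3.5 or 6.9 extra q4w participants with an event, with no difference in risk.

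Variations, for *A* = 13, 26 and 52:

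- *p* = 5% in q8w: 5.6%, 6.2%, 7.4% in q4w.
- 20% annual dropout (*d* = −ln(0.8)/52), with risk λ/(λ + *d*) × (1 − e^(−(λ+d)w)) and λ solved so that q8w still shows 10%: 11.0%, 12.0%, 13.8%.
- Hazard halved after Week 52, that is 1 − 0.9 × e^(−0.5λ(w−52)) averaged over *w*: 10.6%, 11.2%, 12.3%.

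**Pooled column, all guselkumab.** Group 2 starts guselkumab at Week 24, so it has 52 − 24 = 28 weeks by Week 52 and 28 + *U* as written. At *p* = 10%, its risk by 28 weeks is 1 − 0.9^(28/52) = 5.5%. As written it becomes 1 − 0.9448 × (factor above) = 6.8%, 8.0% or 10.3%. With equal group sizes:

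- Week 52 cut for all: (10 + 5.5 + 10)/3 = 8.5%.
- As written: the mean of 10%, group 2 and group 4 is 9.3%, 10.1% or 11.6%.

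**The case against.** The strongest reply is that this is leftover wording and any careful programmer would cut at Week 52. The heading, the scope sentence, two group definitions and the rule in 5.4.1.3 all point there. Harm requires someone to follow the group bullets against the scope sentence, later data to be in the analysis set, and nobody to notice. Average weeks of follow-up appear in every AE table, so an imbalance would be visible. No formal comparison is made, and every rate used to size the effect is assumed.

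Much of this stands. Week 52 is very probably the intended rule, the size cannot be taken from the documents, and the displayed follow-up is a real safeguard. Two supporting points also carry limited weight. The Week 24 sentence on similar follow-up is about placebo, and Protocol 2.2.1.1.3 describes earlier studies and gives rates per 100 subject-years as well as proportions. The pooled guselkumab column mixes 28 and 52 weeks even with a uniform Week 52 cut.

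None of it removes the contradiction. The bullets are the specific statements of follow-up that 5.4.2 relies on, and the longer cut-off is written three times, only in the q4w groups. Showing average follow-up may reveal an imbalance but does not correct the percentages, and 5.4.3 specifies no exposure-adjusted rates.

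**Conclusion.** The concern holds. SAP 5.4.1.2 contradicts itself on the Week 52 safety cut-off, and no other section resolves it. If the group definitions are programmed as written and post-Week 52 data are in the locked database, crude q4w percentages can only move upward relative to q8w. With equal constant hazards, no dropout and uniform accrual over 13 to 52 weeks, 10% in q8w would show as 11.2% to 14.6% in q4w. Dropout or a falling hazard makes the gap smaller, and cutting at each participant's Week 52 makes it zero. The text mismatch is certain; the size depends on assumptions.

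The consequence is confined to the descriptive Week 52 safety tables, including the pooled q4w and all-guselkumab columns. The Week 24 tables, the end-of-study tables and all efficacy tests are unaffected. It should be corrected, but it does not threaten the trial's main conclusions.

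**What to change.** In SAP 5.4.1.2, change *end of study* to *Week 52* at the two places in the group 2 definition and the one place in the group 4 definition. All groups then share the cut-off in the section's scope sentence, and 5.4.1.3 produces the end-of-study tables by its substitution without further edits. The cost is three phrase replacements in one section, with no new data and no new analysis.

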5.4.1.3. Summaries Through End of Study

Safety data through End of Study (Week 112) will be analyzed similarly to safety data through Week 52, replacing Week 52 with End of Study.

5.4.2. Extent of Exposure and Study Follow-up

The number and percentage of participants who receive study intervention will be summarized. Descriptive statistics for duration study intervention (N, mean, SD, median, and range (minimum, maximum)) will be summarized.

Study intervention duration is defined as (date of last dose of study intervention – date of first dose of study intervention) +1. For the placebo intervention group which has planned crossover at Week 24, the study intervention duration prior to first guselkumab dose will be summarized separately to the study intervention duration on/after first guselkumab dose.

Study follow-up duration is defined in Section 5.4.1.

Study intervention compliance will be summarized descriptively. See Section 6.6 for further details.

5.4.3. Adverse Events

The verbatim terms used in the eCRF by investigators to identify AEs will be coded using the Medical Dictionary for Regulatory Activities (MedDRA). Any AE occurring at or after the initial administration of study intervention and those AEs that were present at baseline but worsened in severity after the start of initial study intervention are considered to be treatment emergent. If the event occurs on the day of the initial administration of study intervention, and either event time or time of administration are missing, then the event will be assumed to be treatment emergent. If the event date is recorded as partial or completely missing, then the event will be considered to be treatment emergent unless it is known to be prior to the first administration of study intervention based on partial onset date or resolution date. All reported treatment-emergent adverse events will be included in the analysis. For each adverse event, the number and percentage of participants who experience at least 1 occurrence of the given event will be summarized by intervention group.

Summary tables will be provided for treatment-emergent adverse events:

- Treatment emergent adverse events (TEAEs)
- Treatment emergent SAEs
- TEAEs with severe intensity
- TEAEs leading to permanent discontinuation of study intervention
- TEAEs reasonably related to study intervention
- SAEs reasonably related to study intervention

- TEAEs leading to dose interruption of study intervention
- Treatment emergent infections
- Treatment emergent serious infections
- Treatment emergent infections requiring oral or parenteral anti-microbial treatment
- Injection-site reactions
- Venous thromboembolism (VTE) events
- Clinically important hepatic disorder events
- Anaphylaxis, hypersensitivity and serum sickness reactions
- TEAEs leading to death

All AE summary tables will include average weeks of follow-up and average number of study intervention for each intervention group.

In addition to the summary tables, listings will be provided for participants who had:

- SAEs
- TEAEs leading to permanent discontinuation of study intervention
- Anaphylactic reactions or serum sickness reactions
- Malignancies
- Serious infections including TB
- TEAEs leading to death
- Venous thromboembolism (VTE) events
- Major adverse cardiovascular events (MACE) events
- Clinically important hepatic disorder events
- Opportunistic infections

Section 6.7 contains the methods of identification for selected AEs of interest.

A listing of participants who died will be provided, including cause of death, date of death, relationship to study intervention, and study day of death in relation to reference date.

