2.2.1.1.3. Safety results

Refer to the latest version of the guselkumab IB for detailed safety results of PSA3001 and PSA3002.

Overall, the guselkumab safety profile in the PsA population was generally comparable with that established in the psoriasis population.

Through 1 year, the pooled safety data from PSA3001 (through Week 60) and PSA 3002 (through Week 52) indicated that both guselkumab dose regimens (ie, 100 mg SC administered at Weeks 0 and 4 and then q8w or q4w) were well tolerated in participants with active PsA. Similar proportions of participants in the guselkumab q8w and q4w groups experienced adverse events (AEs), serious adverse events (SAEs), AEs leading to study discontinuation, AEs with severe intensity, infections, serious infections, and injection-site reactions through 1 year of follow-up. Frequencies of events of suicidal ideation, malignancy, and major adverse cardiovascular events were low and comparable in the guselkumab q8w and q4w groups. There were no events of opportunistic infections, active tuberculosis (TB), anaphylaxis or serum sickness reactions, or suicidal behavior or self-injurious behavior without suicidal intent in guselkumab-treated participants in either of the PSA3001 or PSA3002 studies through 1 year. The proportion of participants experiencing increases in transaminases was slightly higher in the guselkumab q4w group compared with the g8w group. In addition, the number of participants with AEs, SAEs, AEs leading to discontinuation of study intervention, infections, and serious infections per 100 subject-years of follow-up were generally comparable between the guselkumab 100 mg q8w and q4w groups through 1 year and the placebo-controlled period through Week 24.

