At Week 16, all participants in Groups I, II, and III with <20% improvement from baseline in both tender and swollen joint counts will qualify for early escape and will be allowed to initiate or increase the dose of one of the permitted concomitant medications up to the maximum allowed dose as specified in Table 3, as selected by the investigator.

At Week 24, all participants in the placebo group (Group III) will cross over in a blinded fashion to receive guselkumab 100 mg SC q4w through Week 100; this will allow for collection of additional safety data for the guselkumab 100 mg SC q4w dose. Participants in the guselkumab groups (Groups I and II) will remain on the dosing regimen they were randomized to at Week 0, through Week 100.

Database locks (DBLs) are scheduled at Week 24, Week 52 and the end of the study (Week 112). The first DBL will occur when all randomized participants have either completed the Week 24 assessments or terminated study participation prior to the Week 24 visit (referred to as Week 24 DBL). The second DBL will occur when all randomized participants have either completed the Week 52 assessments or terminated study participation prior to the Week 52 visit (referred to as Week 52 DBL). The third DBL will occur when all participants have either completed their final safety visit or have terminated study participation (referred to as Final DBL).

The end of study is considered as the last visit for the last participant in the study.

A diagram of the study design is provided in Section 1.2, Schema.

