1.2. Study Design

[figure not shown]
This is a Phase 3b, multicenter, randomized, double-blind, placebo-controlled interventional study in participants with active PsA who had an inadequate response and/or intolerance to one prior anti-TNF.

A target of 450 participants will be randomly assigned in this study with 150 participants planned per intervention group: guselkumab q8w (n=150), guselkumab q4w (n=150), or placebo (n=150).

Stable doses of concomitant non-steroidal anti-inflammatory drugs (NSAIDs), oral corticosteroids (≤10 mg/day prednisone equivalent) and selected non-biologic DMARDs (methotrexate [MTX], sulfasalazine [SSZ], hydroxychloroquine [HCQ], leflunomide [LEF]) will be allowed but are not required.

There will be a screening phase of approximately 6 weeks, a treatment phase of approximately 2 years that will include a double-blind placebo-controlled period from Week 0 to Week 24 and an active controlled treatment phase from Week 24 to Week 100, and a safety follow-up at Week 112 (approximately 12 weeks after the last intended dose at Week 100 per protocol).

An overview of the study design is provided in Figure 1.

medications up to the maximum allowed dose, as selected by the investigator.

At Week 0, participants who satisfy all inclusion and exclusion criteria will be randomly assigned to 1 of the following 3 treatment groups in a 1:1:1 ratio using permuted block randomization stratified by baseline non-biologic DMARD use (yes/no).

- Group I (n=150), guselkumab 100 mg SC every 8 weeks (q8w): Participants will receive SC guselkumab 100 mg at Weeks 0, 4 then q8 at Weeks 12, 20, 28, 36, 44, 52, 60, 68, 76, 84, 92, and 100. Participants will receive placebo SC at Weeks 8, 16, 24, 32, 40, 48, 56, 64, 72, 80, 88, and 96 to maintain the blind.
- Group II (n = 150), guselkumab 100 mg SC every 4 weeks (q4w): Participants will receive SC guselkumab 100 mg at Weeks 0, 4, then q4 at Weeks 8, 12, 16, 20, 24, 28, 32, 36, 40, 44 48, 52, 56, 60, 64, 68, 72, 76, 80, 84, 88, 92, 96, and 100.
- Group III (n=150), placebo and placebo cross-over: Participants will receive SC placebo at Weeks 0, 4, 8, 12, 16 and 20, and will cross over at Week 24 to receive SC guselkumab

3

[†] The first DBL will occur when all randomized participants have either completed the Week 24 assessments or terminated study participation prior to the Week 24 visit.

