[‡] The second DBL will occur when all participants have either completed their final safety visit or have terminated study participation.

100 mg at Weeks 24, 28, then q4w at Weeks 32, 36, 40, 44, 48, 52, 56, 60, 64, 68, 72, 76, 80, 84, 88, 92, 96, and 100.

At Week 16, all participants in Groups I, II, and III with <20% improvement from baseline in both tender and swollen joint counts will qualify for early escape (EE) and will be allowed to initiate or increase the dose of one of the permitted concomitant medications up to the maximum allowed dose as specified in Table 2, as selected by the investigator.

Table 2: Permitted Concomitant Medications for PsA and the Maximum Allowed Doses During the Study				
Permitted Concomitant Medications for PsA ^a	Maximum Allowed Dose			
NSAIDs and other analgesics	Marketed dose approved in in the country where the study is being conducted			
Oral corticosteroids	Equivalent to 10 mg/day of prednisone			
Methotrexate (MTX) ^b	25 mg/week			
Sulfasalazine (SSZ)	3 g/day			
Hydroxychloroquine (HCQ)	400 mg/day			
Leflunomide (LEF)	20 mg/day			

^a Permitted concomitant medication are not supplied by the Sponsor.

At Week 24, all participants in the placebo group (Group III) will cross over in a blinded fashion to receive guselkumab 100 mg SC q4w through Week 100; this will allow for collection of additional safety data for the guselkumab 100 mg SC q4w dose. Participants in the guselkumab groups (Groups I and II) will remain on the dosing regimen they were randomized to at Week 0, through Week 100.

Database locks (DBLs) are scheduled at Weeks 24, Week 52, and the end of the study (Week 112). The first DBL will occur when all randomized participants have either completed the Week 24 assessments or terminated study participation prior to the Week 24 visit (referred to as Week 24 DBL). The second DBL will occur when all randomized participants have either completed the Week 52 assessments or terminated study participation prior to the Week 52 visit (referred to as Week 52 DBL). The third DBL will occur when all participants have either completed their final safety visit or have terminated study participation (referred to as Final DBL).

The end of study is considered as the last visit for the last participant in the study.

Blinding

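### In the Week 52 and end-of-study AE tables, the columns containing crossover participants carry less follow-up than q8w but are given only as crude percentages, so with a common cut-off q4w Combined reads low at equal risk

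*SAP*

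**What the plan says.** **Crossover.** At Week 24, "all participants in the placebo group (Group III) will cross over in a blinded fashion" to q4w (SAP 1.2). Protocol 4.1 gives the reason: "this will allow for collection of additional safety data for the guselkumab 100 mg SC q4w dose".

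**Columns.** SAP 5.4.1.2 opens with "Safety data through Week 52 will be analyzed according to the following intervention groups" and sets out six columns: Placebo, Placebo→q4w (Group 2), q8w (Group 3), q4w (Group 4), q4w Combined and All Combined. q4w Combined is defined as "Participants in Groups 2 and 4", that is, crossover plus randomised q4w. All Combined adds q8w. The clock for Placebo→q4w starts at the first guselkumab dose. SAP 5.4.1.3 repeats the scheme to Week 112.

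**End of follow-up.** Within 5.4.1.2, q8w follow-up stops at Week 52, while Groups 2 and 4 are followed to the end of the study.

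**Measure.** SAP 5.4.3 specifies "the number and percentage of participants who experience at least 1 occurrence of the given event will be summarized by intervention group". It adds: "All AE summary tables will include average weeks of follow-up and average number of study intervention", per group. No rate per participant-year and no time-to-event summary of AEs is planned. SAP 5.4 plans no formal safety comparison. Only the Week 24 tables (5.4.1.1) are described as resting on similar follow-up across groups.

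**Earlier studies.** Protocol 2.2.1.1.3 describes the two earlier Phase 3 studies by proportions and, in addition, by participants with events, which "per 100 subject-years of follow-up were generally comparable between the guselkumab 100 mg q8w and q4w groups".

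**The concern.** A percentage with at least one event rises with time observed. Crossover participants have 24 weeks less guselkumab follow-up than those randomised to guselkumab, and they make up half of q4w Combined and a third of All Combined. Those columns stand beside q8w with no measure that allows for the shortfall.

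q4w Combined is also the column that uses the q4w data the crossover was meant to add. Protocol 2.2.1.1.3 notes slightly more transaminase increases with q4w than with q8w, so a q4w column that reads low by construction leans towards reassurance. The different end points in 5.4.1.2 add a second problem: as worded, it is unclear which way the Week 52 columns lean.

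**Working it through.** **Figures in the plan.** The documents give no AE rate and no AE precision, so there is no safety figure to reproduce. The only stated figure behind the group size is ACR 20 power above 99% with 150 per group. It reproduces (99.98%, above 99.99% and 99.65% for the three scenarios) but does not bear on this point.

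**Inputs.**
- Group size: "with 150 participants planned per intervention group" (SAP 1.2).
- Crossover at Week 24; cut-offs at Week 52 and Week 112 (SAP 1.2, 5.4.1.2, 5.4.1.3).
- Assumptions: one cut-off for all groups, the same constant hazard in every group, full planned follow-up, and AE rates of 5 to 100 per 100 person-years.

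**Planned follow-up.**
- To Week 52: crossover 52 − 24 = 28 weeks; q8w and randomised q4w 52. Mean in q4w Combined (28 + 52)/2 = 40, in All Combined (28 + 52 + 52)/3 = 44.
- To Week 112: crossover 112 − 24 = 88 weeks; q8w and randomised q4w 112. Mean in q4w Combined (88 + 112)/2 = 100, in All Combined (88 + 112 + 112)/3 = 104.

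**Formula.** P(at least one event) = 1 − exp(−rate × weeks/52.18), with the rate per person-year. The q4w Combined percentage is the mean of the crossover and randomised q4w percentages, weighted by group size.

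Example at 5 per 100 person-years, Week 52: crossover 1 − exp(−0.05 × 28/52.18) = 2.65%; q4w and q8w 1 − exp(−0.05 × 52/52.18) = 4.86%; q4w Combined 3.75%; ratio to q8w 0.77.

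| Cut-off | Rate per 100 PY | Crossover % | Randomised q4w % | q4w Combined % | q8w % | Combined/q8w |
|---|---|---|---|---|---|---|
| Week 52 | 5 | 2.65 | 4.86 | 3.75 | 4.86 | 0.77 |
| Week 52 | 20 | 10.18 | 18.07 | 14.12 | 18.07 | 0.78 |
| Week 52 | 100 | 41.53 | 63.08 | 52.31 | 63.08 | 0.83 |
| Week 112 | 5 | 8.09 | 10.18 | 9.13 | 10.18 | 0.90 |
| Week 112 | 20 | 28.63 | 34.90 | 31.77 | 34.90 | 0.91 |
| Week 112 | 100 | 81.48 | 88.31 | 84.90 | 88.31 | 0.96 |

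Randomised q4w equals q8w in every row.

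**What the gap could hide.** For rates of 2 to 100 per 100 person-years, q4w Combined and q8w would show equal percentages if the true q4w hazard were 1.30 to 1.36 times that of q8w (Week 52) or 1.12 to 1.14 times (end of study).

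**Fewer crossing over.** With 120 instead of 150 (an assumed 20% loss before Week 24), the ratios at 5 to 100 per 100 person-years become 0.80–0.85 at Week 52 and 0.91–0.97 at end of study.

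**Literal reading of 5.4.1.2.** If Groups 2 and 4 run to the end of the study in the Week 52 table, their follow-up is 88 and 112 weeks (mean 100) against 52 for q8w. At 5 per 100 person-years q4w Combined shows 9.1% against 4.9%, and at 100 it shows 84.9% against 63.1%. The direction reverses.

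**With the fix.** The rate is participants with a first event divided by person-years to first event or cut-off. Under the same assumptions, q4w Combined and q8w give 5.0 and 5.0, or 100 and 100, per 100 person-years at both cut-offs.

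**The case against.** The strongest reply is that the fair dose comparison is already in every table. Randomised q4w has its own column, with the same planned follow-up as q8w under a common cut-off. That stands in full. A reader might infer that these tables make the q4w regimen look safer than q8w. The documents do not support this for the randomised arm; only columns containing crossover participants are affected.

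A reader might also infer that the later tables set 24 weeks of placebo against up to 112 weeks of guselkumab and so exaggerate harm. SAP 5.4.1.1 bases between-group comparison with placebo on the Week 24 table, where follow-up is similar. The SAP makes no such claim for the later tables.

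Nor do the documents show that a planned measure was dropped. Subject-year rates were reported for earlier studies, alongside proportions. Protocol 9.4.4 plans percentages for this trial and the SAP follows it. Likewise, the crossover is described as a way to collect more q4w safety data, not as a dose comparison.

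Average weeks of follow-up are printed in each AE table, and the safety analysis is descriptive. This discloses the imbalance, and for uncommon events it allows a rough rate. It does not correct the percentage, and it gives neither time at risk to first event nor a confidence interval. Descriptive columns placed side by side will still be compared.

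Finally, a constant hazard overstates the gap for events that occur soon after starting treatment, such as injection-site reactions. That also stands.

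**Conclusion.** The point holds for Placebo→q4w, q4w Combined and All Combined in the Week 52 and end-of-study AE tables. With a common cut-off, equal constant hazard and 150 per group, q4w Combined reads about 17–23% low relative to q8w at Week 52 and 4–10% low at end of study, for assumed rates of 5 to 100 per 100 person-years. The gap shrinks with fewer crossovers, early-onset events or very common events.

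The end-of-study result does not depend on the wording of 5.4.1.2. The Week 52 direction does, and that section conflicts with its own stated period. Randomised q4w against q8w and the Week 24 placebo comparison are sound as planned. This is a cheap improvement to descriptive tables, not a flaw in the randomised safety comparison.

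**What to change.** 1. In SAP 5.4.3, for each column of the Week 52 and end-of-study AE summary tables, add participants with a first event per 100 participant-years at risk, with 95% CI. Keep the percentages and the average weeks of follow-up.
2. State that the pooled columns are to be read from these rates, and name randomised q4w against q8w as the dose comparison. The second statement matters because the rates match exactly only under a constant hazard. Where events cluster early, pooling different lengths of follow-up still mixes different times since first dose.
3. Reconcile SAP 5.4.1.2 so that all groups in the Week 52 tables have one cut-off.
4. Malignancy and MACE are only listed in 5.4.3, so rates for them would need a small added table.

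The cost is SAP wording and longer tables. Follow-up is already defined by group, but time to first event must be derived for each event category. No new data are needed.
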